### **5 STUDY OUTCOME MEASURES FOR PHASE 2**

#### **5.1 Primary**

- a) POM 1.1: Proportions of appropriate overall site of care disposition with or without EHR-based prognostic decision support in children 0.6-17 years presenting for emergency care. Please see Appendix 2 for the definition of appropriate site of care disposition (an investigator in both Nashville and Pittsburgh will be in charge of review, blinded to intervention assignment).

#### **5.2 Secondary**

- a) SOM 1.1: Proportions of appropriate site of care disposition, by EHR-based prognostic decision support or usual care.
- b) SOM 2.1: Proportions of participants having ED revisits within 72 hours of the index discharge, by EHR-based prognostic decision support or usual care.  
SOM 2.2: Proportions of participants having hospitalizations within 72 hours of the index discharge, by EHR-based prognostic decision support or usual care.
- c) SOM 3.1: Proportions of participants having ED revisits within 7 days of the index discharge, by EHR-based prognostic decision support or usual care.  
SOM 3.2: Proportions of participants having hospitalizations within 7 days of the index discharge, by EHR-based prognostic decision support or usual care

#### **5.3 Exploratory**

- a) EOM 1.1: Proportion of death, by EHR-based prognostic decision support or usual care.
- b) EOM 2.1: Hospital length of stay among hospitalized children, by EHR-based prognostic decision support or usual care.

## **6 STUDY DESIGN**

### **6.1 Study Description**

Extensive variation in both antibiotic use and hospitalization decisions is evident among clinicians caring for children with pneumonia, with high potential for avoidable harm. In our prior study, one-third of children were hospitalized for less than 48 hours and nearly 10% less than 24 hours. Some of these hospitalizations were likely unnecessary. Most of these children also received broad-spectrum antibiotic therapy instead of the narrow-spectrum agents recommended by the national guideline. Conversely, one-third of children admitted to intensive care were initially managed on a general ward—earlier transfer for more intensive therapy may have improved outcomes for some of these children. New strategies to inform decision making are needed, and the combination of risk stratification using objective tools and clinical decision support in the ED setting are innovative and promising approaches to achieve this goal.

#### **6.1.1 Phase 1**

To test the hypothesis that electronic antibiotic decision support increases guideline-concordant antibiotic use compared with usual care in the ED.

The primary outcome is the proportion of children exclusively receiving guideline-concordant 1st line antibiotic therapy during the first 24 hours of care (Table 1). Secondary outcomes include exclusive use of guideline-concordant antibiotic therapy for the entire episode, any use of concordant antibiotic therapy during the first 24 hours of care and for the entire episode, and ED revisits and hospitalizations within 72 hours and 7 days of the index discharge.

#### **6.1.2 Phase 2**

To test the hypothesis that the delivery of severity information generated by our prognostic tool leads to more appropriate site of care disposition compared to usual care.

The primary outcome is appropriate site of care disposition (Table 2). Surveillance for subsequent ED visits and hospitalizations to our institutions as well as escalation to higher levels of care will be captured within the EHR data extracted by the decision support application. Secondary efficacy and safety outcomes include the overall site of care disposition (ED discharge, ward, ICU), and ED revisits and hospitalizations within 72 hours and 7 days of the index discharge.

## **6.2 Sample Size and Power**

### **6.2.1 Phase 1**

Based on ED and hospitalization data from our hospitals during the conduct of the EPIC study, we anticipate nearly 2000 total children with pneumonia will be evaluated annually during the conduct of these studies. Assuming conservatively that data for 750 children are enrolled in each arm, and 30% guideline-concordant antibiotic use in the usual care arm (based on our prior study of antibiotic use in the EPIC cohort), we will be able to detect an absolute difference of  $\geq 6.8\%$  in guideline-concordant prescribing at an alpha level of 0.05 with 80% power. Effective sample size may be reduced due to the cluster randomized nature of the study (a conservative estimate for effective sample size would be around 500 children in each arm).

### **6.2.2 Phase 2**

As outlined in P1, we anticipate nearly 2000 children with pneumonia will be evaluated annually during the conduct of these studies. Assuming conservatively that data for 2000 children (1000 in each arm) are captured during the two-year study period, and 90% appropriate site of care disposition in the usual care arm (based on data from the EPIC cohort), we will be able to detect an absolute difference of  $\geq 3.4\%$  in appropriate care disposition at an alpha level of 0.05 with 80% power.

## **6.3 Randomization**

### **6.3.1 Phase 1**

During the 18-month study period, EHR-based antibiotic decision support will be active monthly (4-week blocks) based on the cluster randomized scheme at each hospital. To ensure balanced representation of each arm in periods of both low and high pneumonia prevalence, randomization will occur in 3 permuted blocks (size=6). The antibiotic decision support application will be provided to those randomized to the intervention arm, whereas the control arm will receive usual care. Participants enrolled during the month with antibiotic decision support will be assigned to the intervention arm, and participants receiving usual care will be in the control arm. Participants will be blinded to the treatment assignments and study staff and providers will not be blinded to treatment arm assignments due to the nature of the interventions.

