4.0 Study Design and Randomization

4.1 Study Design and Randomization (P1, EHR-based antibiotic decision support)

Effectiveness of the EHR-based antibiotic decision support application for promoting guideline-concordant antibiotic prescribing in children presenting for emergency care will be evaluated in a pragmatic, cluster randomized crossover study conducted over a period of 18 months that includes two respiratory seasons. Our institutions possess demonstrated experience in the execution of these pragmatic designs.¹⁷⁻²¹ Crossover will occur each month in a randomly determined sequence within each hospital. To ensure balanced representation of each arm in periods of both low and high pneumonia prevalence, randomization will occur in 3 permuted blocks (size=6). The cluster-randomized crossover design also improves efficiency and reduces potential problems related to cluster imbalance when using a small number of clusters.⁶⁷ The antibiotic decision support application will be provided to those randomized to the intervention arm, whereas the control arm will receive usual care. Due to the nature of the intervention, blinding of treating providers will not be possible. Importantly, since this is a trial focused on provider behavior, all children will receive standard of care management. All treatment decisions will be made by the clinical providers and will not be restricted or altered in any way.

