An important consideration in our analysis is the possibility of contamination effects in the usual care arm related to changes in provider behavior due to past exposures and awareness of the intervention. Such contamination would be expected to bias toward the null hypothesis. We posit that such effects will be of minor concern since 1) guideline-concordant prescribing at our institutions remains low despite the presence of both national and local practice guidelines and order sets for several years; 2) the ED is a busy environment with many providers (e.g., 40+ ED faculty plus mid-level providers and fellows/residents at Vanderbilt alone), such that repeated exposure to the intervention by any one provider would be infrequent, particularly early during the study period and during times of low pneumonia prevalence; and 3) resident physicians, the providers responsible for the majority of order entry and thus directly exposed to the intervention, rotate on a monthly schedule and only work in the ED once each year. We have designed our randomization and monthly crossover periods around these important considerations. Nevertheless, we acknowledge the potential for contamination, and we will formally evaluate for such effects in a secondary analysis by modeling the monthly proportions of guideline-concordant prescribing in each arm over the duration of the study period. We will then compare prescribing trends in both arms with a historical trend estimated from monthly proportions of guideline-concordant prescribing in the year prior to study initiation. By comparing prescribing trends in each arm to this historical trend, we will estimate both the degree of potential contamination as well as the independent impact of the intervention.

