13.0 Follow-Up and Record Retention

The anticipated study duration is 24 months for P1 and 24 months for P2. As this study does not include direct contact with enrolled subjects, there is no anticipated follow up. Records will be maintained in accordance with IRB, institutional, and sponsor policies.

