### **10.1 Primary Objective**

The primary objective (PO 1) of the study is to compare proportions of participants exclusively receiving guideline-concordant 1st line antibiotic therapy during the first 24 hours of care with or without EHR-based decision support in children 0.6-17 years of age presenting for emergency care. The hypothesis for this primary objective is that the proportion of participants exclusively receiving guideline-concordant 1st line antibiotic therapy during the first 24 hours of care is higher in the group receiving EHR-based decision support vs. the group receiving usual care. This information is captured through chart review and entered in the REDCap database. The antibiotics received by a participant is concordant yes (1) or no (0) based on Appendix 1 table, for this analysis.

The proportions will be compared between the intervention arm versus the control arm using a Cochran-Mantel-Haenszel method in a stratified analysis by site to control for two sites at the alpha 0.05 level. The proportion difference and corresponding 95% confidence interval for concordance of antibiotics with or without adjusting for sites will also be calculated.

We will use a hierarchical and mixed effects logistic regression model, a complex analytic approach which offers flexibility regarding model assumptions and incorporation of cluster-level and individual-level covariates. The outcome is proportions of participants exclusively receiving guideline-concordant 1st line antibiotic therapy during the first 24 hours of care and the main exposure variable is intervention vs. usual care. The month of each participant enrolled will be treated as a random effect. We will also use a weighted, cluster-level logistic regression to compare guideline-concordant antibiotic prescribing between groups. In this analysis, data for each cluster are collapsed into a single summary measure, and the summary measures are then analyzed as if they were raw data, facilitating simple data reporting and interpretation. Important baseline covariates (e.g., age, sex, race, site, season, frequency of bacteremia and other pneumonia-related complications) will also be assessed and included as model covariates.

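### The Phase 1 mixed model takes month of enrolment as its random effect, but the unit randomised is the hospital-period

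*SAP*

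**What the plan says.** **Randomisation.** Protocol section 4.1: "Crossover will occur each month in a randomly determined sequence within each hospital". SAP section 6.3.1: "EHR-based antibiotic decision support will be active monthly (4-week blocks", following a randomised scheme held separately for each hospital. Both give an 18-month Phase 1 and three permuted blocks of size six. Arm follows the period: "Participants enrolled during the month with antibiotic decision support will be assigned to the intervention arm".

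**Mixed model (SAP section 10.1).** "The month of each participant enrolled will be treated as a random effect". No other random effect is named. Site and season enter as covariates: "Important baseline covariates (e.g., age, sex, race, site, season, frequency of bacteremia and other pneumonia-related complications". Month is not defined there as a calendar month or a 4-week block.

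**Other primary analyses (SAP section 10.1).** A Cochran-Mantel-Haenszel (CMH) comparison stratified by site carries the 0.05 alpha level. A weighted cluster-level logistic regression collapses each cluster to one summary value, but does not say what a cluster is.

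**Sample size (SAP section 6.2.1).** 750 children per arm, 30% concordance under usual care, a detectable difference of 6.8 percentage points with 80% power, and a conservative effective size of about 500 per arm because of clustering. No intracluster correlation is given.

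**The concern.** In a cluster crossover trial the standard error of the treatment effect must reflect variation between the units that were randomised. Here the sequences are drawn separately in each hospital, so the unit is one hospital in one period. The named random effect has about 18 levels and ties together the children of both hospitals in the same month. With independent sequences, the hospitals are expected to be in opposite arms in half of the periods. In those periods one shared effect covers two units randomised to different arms. Anything that moves prescribing at one hospital in one period (staffing, local virus activity) is then treated as independent variation between children.

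A second, smaller mismatch appears if month is taken to mean calendar month, because 28-day blocks do not start and end with calendar months.

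At stake are the width of the mixed-model confidence interval for the primary outcome and its false-positive rate. The unit for the cluster-level analysis is also left to the analyst.

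**Working it through.** **1. The plan's own figure.** Two-sided 0.05, 80% power, 750 per arm, 30% against 36.8%, mean 33.4%:

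1.96 × √(2 × 0.334 × 0.666 / 750) + 0.8416 × √((0.30 × 0.70 + 0.368 × 0.632) / 750) = 0.0477 + 0.0204 = 0.068.

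The 6.8% reproduces. At 500 per arm the same calculation gives 8.4%.

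**2. Units.** 3 × 6 = 18 periods per hospital; 2 × 18 = 36 hospital-periods; 1,500 / 36 = 41.7 children each.

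**3. Implied correlation.** Design effect 750 / 500 = 1.5. If it arises wholly from hospital-periods, ICC = (1.5 − 1) / (41.7 − 1) = 0.0123. On the logit scale the between-period SD is about √(0.0123 / 0.21) = 0.24, with 0.21 = 0.30 × 0.70. This ICC is derived under that assumption; the documents do not state it.

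**4. Why a shared month effect misses it.** Take one period with the hospitals in opposite arms. The simple binomial variance of the difference is 2 × 0.21 / 41.7 = 0.0101. With hospital-specific period effects it is 0.0101 × 1.5 = 0.0151. A month effect common to both hospitals cancels from that difference, so it cannot supply the missing part.

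**5. Null simulation.** 1,500 trials per setting; 2 hospitals; 18 four-week periods; permuted blocks of six within hospital; 1,500 children enrolled evenly over time and between hospitals; 30% concordance. Random-intercept logistic models with arm and site fixed, likelihood-ratio test. Monte Carlo standard error is about 0.6 to 1 point. By the formula in step 3, SDs of 0.12, 0.24 and 0.40 correspond to design effects of about 1.1, 1.5 and 2.4.

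Type I error (%) with effects specific to hospital and 4-week period:

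| Analysis | SD 0.12 | SD 0.24 | SD 0.40 |
|---|---|---|---|
| Random effect: calendar month | 4.8 | 10.1 | 17.3 |
| Random effect: 4-week period | 4.6 | 8.7 | 16.6 |
| Random effect: hospital × calendar month | 4.7 | 8.7 | 14.5 |
| Random effect: hospital × 4-week period | 3.9 | 5.1 | 5.2 |
| CMH by site | 5.2 | 10.8 | 19.3 |

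An independent simulation at design effect about 1.5 gave, for the four random effects in the same order, 9.9, 9.7, 9.3 and 6.1%. A smaller run (800 trials, linear model, Wald z test) gave 10.5% for 4-week period and 7.4% for hospital × 4-week period. As an analytic check, a test that ignores a design effect of 1.5 has size 2 × (1 − Φ(1.96 / √1.5)) = 11.0%.

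Type I error (%) at SD 0.24 when the correlation sits elsewhere:

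| Period effects | Calendar month | 4-week period | Hospital × calendar month | Hospital × 4-week period |
|---|---|---|---|---|
| Hospital-specific, calendar month | 6.9 | 6.3 | 5.5 | 5.2 |
| Shared, 4-week | 7.8 | 5.4 | 8.5 | 5.7 |
| Shared, calendar month | 5.2 | 5.1 | 5.5 | 5.5 |

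**6. Period length.** 18 × 28 = 504 days, or 504 / 30.44 = 16.6 months. Eighteen months are about 548 days, which is 44 days more and would hold 548 / 28 = 19.6 blocks. Both documents provide 18 periods.

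**The case against.** **The SAP uses month as its own word for the 4-week block.** This is a fair reading. Section 6.3.1 glosses monthly as 4-week blocks and then assigns arms by month; section 10.1 can be read the same way. So a reader might infer from the 4-week wording alone that the model uses the wrong cluster, but the documents do not support that: it needs a calendar-month definition that neither gives. Changing calendar month to 4-week period also does little by itself (10.1% to 8.7%, and 9.9% to 9.7% in the second simulation). What remains is the absence of hospital from the random effect, which holds under either reading.

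**No ICC is stated, and 500 per arm is called conservative.** This stands. At SD 0.12 all the models are near 5%, and if the effects are common to both hospitals and follow calendar months the month effect is adequate. Any inflation is therefore conditional.

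**The mixed model is not the test tied to alpha 0.05.** Also true. But the site-stratified CMH test takes no account of period and reaches 10.8% under the same assumption, so it gives no protection. Protocol section 8.2 itself says that correlation within clusters and periods must be accounted for, and in the SAP the mixed and cluster-level models are what could do so.

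**Two further inferences go too far.** A reader might conclude that enrolment suffers because 504 days is 8% short of 18 months. At nearly 2,000 children evaluated a year, 504 days would still see about 2,000 × 504 / 365.25 = 2,760, against the 1,500 needed. A reader might also conclude that 4-week blocks defeat the contamination argument in protocol section 8.2, which says that residents "rotate on a monthly schedule and only work in the ED once each year". It does not say that rotations follow calendar months, and rotation is one of three arguments given there.

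**Conclusion.** The point holds as a mis-specified random effect. The randomised unit is the hospital-period, and the model names a month effect with no hospital dimension. If a design effect of about 1.5 comes from hospital-specific period effects, type I error of the mixed model is about 9-10% as written and about 5-6% with hospital × randomised period. Both crossing with hospital and using the true period are needed: hospital × calendar month stays at about 9%.

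A reader might infer that type I error simply exceeds 5%. The documents do not establish that. Under the calendar-month reading, the simulated range is about 5% to 17%, depending on the assumed variance and on whether the effects are hospital-specific or shared. Even enrolment and equal hospitals are also assumed; seasonal enrolment would change the figures.

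Separately, the stated period lengths do not fit together. Eighteen 4-week blocks do not fill 18 months, and protocol section 13.0 gives another duration: "The anticipated study duration is 24 months for P1 and 24 months for P2". That needs reconciling but does not drive the error rate.

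**What to change.** - In SAP section 10.1, replace month of enrolment with the randomised hospital-period as the random effect: 36 levels, read from the randomisation list, with hospital as a fixed effect.
- In the weighted cluster-level analysis, define the cluster as the same 36 hospital-periods, so that both models rest on one unit.
- State one period length, with start and end dates, in protocol section 4.1 and SAP section 6.3.1. Reconcile it with the 18-month duration and with protocol section 13.0.

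The cost is a change of wording; no new data are needed. The confidence interval will be somewhat wider if hospital-specific period variation is present.

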### **6.3.2 Phase 2**

During the 24-month study period, randomization will occur at the patient level. Allocation to intervention or control will be based on medical record number (even vs. odd) and will be assigned automatically once the treating provider confirms the diagnosis of pneumonia and eligibility. We expect participants will be randomized (1:1). The providers of intervention subjects will receive prognostic information derived using our previously validated and best performing model. Providers of control arm subjects will not receive this information but will have access to all clinical data. Participants will be blinded to the treatment assignments and study staff and providers will not be blinded to treatment arm assignments due to the nature of the interventions.

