In these studies, conducted at two experienced academic centers, we will implement and evaluate an EHR-based clinical decision support application to promote antibiotic use in concordance with the 2011 PIDS/IDSA guideline in a pragmatic, cluster-randomized crossover trial (P1). Next, we will incorporate risk stratification using a previously developed prognostic tool into a second EHR-based decision support application, testing its impact on site of care disposition compared to usual care in a pragmatic randomized trial (P2). In both studies, all subjects will receive standard of care. Decisions regarding management, including antibiotic selection and site of care, will be at the discretion of the treating provider and will not be restricted or altered in any way. Thus, this study poses no greater than minimal risks to participants. Due to the nature of the research, we will seek a waiver of informed consent as has been done in similar pragmatic studies at our institutions.¹⁷⁻²¹

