4.2 Study Design and Randomization (P2, EHR-based risk stratification)

We will conduct a randomized controlled trial comparing our prognostic tool (intervention arm) to usual care (control arm) over a period of 24 months. Randomization will occur at the patient level. Allocation to intervention or control will be based on medical record number (even vs. odd) or similar strategy and will be assigned automatically once a provider confirms the diagnosis of pneumonia. Importantly, all standard of care treatment options will be available and decision-making will not be restricted in any way in either group. A similar randomized trial that predicts readmission risk among all hospitalized adults using EHR inputs is currently ongoing at Vanderbilt. In that study, every adult admitted to Vanderbilt University Hospital is enrolled (under waiver of consent). Readmission risk is calculated automatically for all patients, but only displayed for a random half to determine if providing this additional information improves outcomes compared to usual care.

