5.0 Inclusion/Exclusion Criteria (Phases 1 and 2)

Inclusion Criteria

1. Six months to <18 years of age
2. Radiographic evidence of pneumonia in ED
3. Provider-confirmed diagnosis of pneumonia

Exclusion Criteria (Provider query and/or automated data abstraction)

1. Children with tracheostomy, cystic fibrosis, immunosuppression
2. Inter-hospital transfers
3. Hospitalization within preceding 7 days
4. Previously enrolled within preceding 28 days
5. Provider preference for any reason

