6.0 Screening and Enrollment

6.1 Screening and Enrollment (P1)

Children with pneumonia presenting to the ED at Monroe Carell Jr. Children's Hospital at Vanderbilt or Children's Hospital of Pittsburgh will be potentially eligible for study. The pneumonia radiology alert tool will be used to identify potentially eligible children in a systematic and efficient manner using natural language processing (NLP). Those who screen positive according to the radiology NLP algorithm will trigger a Best Practice Alert (BPA) or similar within the EHR which queries the provider to confirm the diagnosis of pneumonia and assesses for study inclusion/exclusion criteria. In instances where a chest radiograph is not captured via the NLP algorithm (e.g. a radiograph obtained at an outside facility), an alternative pathway is available to trigger the subsequent BPAs leading to enrollment. Due to the nature of the research, we will seek a waiver of informed consent as has been done in similar pragmatic studies at our institutions.¹⁷⁻²¹ Thus, at this point, eligible children will be considered enrolled. During intervention periods, providers caring for enrolled children will be presented with a detailed decision support strategy that emphasizes management in accordance with national guideline recommendations. During control periods, no additional decision support will be provided.

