6.2 Screening and Enrollment (P2)

Screening and enrollment procedures for P2 will be identical to P1. For children randomized to the intervention arm, providers will be presented with prognostic information regarding risk for severe disease outcomes via an EHR-based decision support strategy that emphasizes management in accordance with national guideline recommendations. During control periods, no additional decision support will be provided.

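### Phase 2 is called randomized, but the arm is set by odd or even record number, so it can be read before a child is enrolled or declined

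*SAP*

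**What the plan says.** SAP 6.3.2 is headed as randomization and places it at the patient level, but the only mechanism it gives is: "Allocation to intervention or control will be based on medical record number (even vs. odd) and will be assigned automatically". Protocol 4.2 is looser: "Allocation to intervention or control will be based on medical record number (even vs. odd) or similar strategy". The alternative is not named, and the SAP drops it. Protocol 2.0 describes the phase as "testing its impact on site of care disposition compared to usual care in a pragmatic randomized trial (P2").

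The arm is released automatically after the provider confirms diagnosis and eligibility. Protocol 6.2 states: "Screening and enrollment procedures for P2 will be identical to P1". Under Protocol 6.1, the alert "queries the provider to confirm the diagnosis of pneumonia and assesses for study inclusion/exclusion criteria". One listed exclusion in Protocol 5.0 is "Provider preference for any reason". That section also allows some exclusions to be found by automated abstraction: "Exclusion Criteria (Provider query and/or automated data abstraction".

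SAP 6.3.2 says providers and study staff are not blinded to arm. SAP 8.1 limits the intent-to-treat population to enrolled, randomized children, and SAP 9.2 plans a flow chart of enrolled children by site and arm. In the text reviewed, neither document mentions allocation concealment or a tabulation of declined children. Protocol 8.6 defends individual allocation on contamination grounds only and does not discuss selection at enrolment.

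**The concern.** Automatic release after confirmation stops anyone changing an assignment by hand. It does not hide a rule that can be worked out from the chart beforehand. The record number exists before the alert fires, and the person answering the alert decides whether the diagnosis is confirmed and may opt the child out.

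Bias in the primary comparison needs three things together: some providers know or infer the rule, they decline more often in one arm, and the declined children differ from average in their risk of an inappropriate disposition. If all three hold, the bias can go in either direction. Because the flow chart and the analysis population both start at enrolment, little in the planned reporting would reveal it. A trial labelled randomized but allocated by parity is open to challenge on this point even if no selection took place.

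There is a smaller, related issue. Outcome review is stated to be blinded (Protocol 7.5, SAP 5.1 and 11.1), but under parity any reviewer who sees the record number can work out the arm.

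**Working it through.** **Inputs from the documents** (SAP 6.2.2, Protocol 8.4): 1000 children per arm, 90% appropriate disposition under usual care, alpha 0.05, 80% power, detectable difference 3.4 points. Sidedness is not stated; I take it as two-sided.

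**The plan's own figure.** A pooled two-proportion z test of 90% v 93.4% with 1000 per arm has power 78.7%, and 80% power is reached at 3.45 points. The stated 3.4 points is therefore reproduced, and this concern does not alter it.

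**Assumptions.** No document gives a decline rate. I assume 1000 eligible children per arm, no true effect, a fraction d declined in one arm only, and a fraction q of those declined who would have had an inappropriate disposition.

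**Size of the bias.** Each arm starts with 100 inappropriate dispositions (10% of 1000). In the arm with selective declining:

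rate = 1 − (100 − 1000·d·q) / (1000·(1 − d)), compared with 90.0% in the other arm by the pooled z test.

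Example with d = 5%, q = 40%: 1 − (100 − 20)/950 = 91.58%, a difference of +1.58 points.

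| d | q | Rate | Difference (points) | Type I error |
|---|---|---|---|---|
| 2% | 0% | 89.80% | −0.20 | 0.053 |
| 2% | 10% | 90.00% | 0.00 | 0.050 |
| 2% | 20% | 90.20% | +0.20 | 0.053 |
| 2% | 40% | 90.61% | +0.61 | 0.075 |
| 5% | 0% | 89.47% | −0.53 | 0.067 |
| 5% | 10% | 90.00% | 0.00 | 0.050 |
| 5% | 20% | 90.53% | +0.53 | 0.068 |
| 5% | 40% | 91.58% | +1.58 | 0.225 |

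To produce the full 3.4 points at d = 5%, the inappropriate rate among the 950 enrolled must fall to 6.6%. That requires q = (100 − 0.066 × 950)/50 = 0.746, or about 75%.

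**Would enrolled counts show it?** Test the split against 1:1 with z = (difference in counts)/√(total).
- 980 v 1000: z = 20/√1980 = 0.45, power 0.07.
- 950 v 1000: z = 50/√1950 = 1.13, power 0.20.
- With a further 10% declined in both arms, 880 v 900: z = 0.47, power 0.08; 850 v 900: z = 1.20, power 0.22.

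**Would declined children by parity show it?** Take 1000 alerted children per parity and 10% background declining.
- 12% v 10%: power 0.30.
- 15% v 10%: power 0.92.
- With no background declining, 20 v 0 or 50 v 0 gives Fisher p < 0.001.

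Data collection is triggered by the alert (Protocol 7.3 through 7.6; SAP 7.1), so this count may be obtainable, but no such check is planned.

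**The case against.** The strongest reply is that nobody has shown providers know the rule. They are unblinded because they see the display, and they see it only after confirming eligibility. Protocol 8.2, writing about Phase 1, describes more than 40 ED faculty at one site and residents who rotate monthly, so few individuals would see enough cases to infer parity. The intervention only shows information, so the motive to decline by arm is weak. On the figures above, most scenarios barely move the type I error; only the most extreme reaches 0.225, and it needs declined children at four times the average risk. The covariate adjustment in SAP 11.1 might absorb part of any imbalance. The Protocol's wording leaves room for another method, and the SAP narrows it without contradicting it. Protocol 10.0 already codes data by study ID.

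Much of this stands, and it bears on likelihood and size: the arm is knowable, not shown to be known. It does not supply concealment or make parity a random draw. Adjustment for measured covariates cannot be relied on to remove selection on a provider's judgement. Study-ID coding does not settle what a reviewer sees during chart review, although chart review could expose the decision-support display under any allocation method.

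One limit on the proposed check also stands. Protocol 6.1 has an alternative enrolment pathway for radiographs that the language-processing screen misses. A child for whom it is never triggered would not be counted among the declined, so the 30-92% detection figures assume that selection happens at the alert.

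**Conclusion.** The concern holds and should be fixed. The SAP's Phase 2 allocation is deterministic and readable before the enrolment decision, no concealment is described, and the planned reporting starts after the point where selection could occur. The text supports this firmly. The harm is conditional and, on the assumed rates, mostly small: +0.2 to +1.6 points if 20-40% of the declined would be inappropriate, zero if they are at average risk, and −0.2 to −0.5 points if none would be. These figures rest on assumed one-arm declining of 2-5% and on the planned 1000 per arm and 90% rate. The case for acting is that the bias would seldom be visible and the remedy is cheap.

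**What to change.** **Allocation.** In Protocol 4.2 and SAP 6.3.2, replace parity and its unnamed alternative with one method: a concealed, EHR-generated, site-stratified 1:1 random assignment, released only after diagnosis and eligibility are locked. State whether a child who re-enrols (possible after 28 days under Protocol 5.0) keeps the first assignment or receives a new draw.

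**Flow chart.** In SAP 9.2, add children who triggered the alert but were declined, by site.

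**If parity is kept.** State how the rule is hidden from treating providers, and report declined children by parity as a check for selection.

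**Secondary.** Give outcome reviewers study-ID-keyed material without the record number or decision-support fields. Reconcile Protocol 7.5, which limits review to short stays, with SAP 11.1, which states no such limit.

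**Cost.** Planned n and power are unchanged. Assignment is already automatic, and Protocol 4.2 describes an ongoing trial at one site in which "Readmission risk is calculated automatically for all patients, but only displayed for a random half". How that half is drawn is not stated, so a modest build change is my assumption. Masked extracts under Protocol 7.5 would cover roughly 1000 × 0.31 × 0.10 = 31 short stays per arm, 62 in total. The range is 38 to 138, using the 19-69% admission rates in Protocol 1.0. This combines an admission rate and a short-stay share from different sources, so it is only indicative. Short ICU stays would be extra, and the total could reach 2000 if SAP 11.1 means every disposition is reviewed.

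There are two downsides. A random draw could move a re-enrolled child to the other arm unless the first assignment is carried forward, which parity avoids. Declined children would have no arm, so they could be reported by site only.
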